We propose a pilot and feasibility trial to use continuous glucose monitoring (CGM) in youth with type 2 diabetes (T2D) and public insurance. This feasibility trial would fill a gap in the literature with respect to CGM use in youth with type 2 diabetes. The findings from this trial can provide much needed data to pave the way for future studies using CGM technology in this population. Our proposal is focused on youth with public insurance, seeking to provide diabetes technology for patients and their families to use in daily diabetes management. This pilot is an expansion of our existing program of CGM access to youth with type 1 diabetes which has led to an improvement HbA1C of 0.5% over 1 year and positive feedback from patients and families.^{1,2}

Specific Aim 1: Evaluate the feasibility of CGM start and continuation in youth with T2D and describe glucose metrics and patient reported outcomes (PROs). We will pilot and refine a program to test the hypothesis that CGM start and continuation in youth with T2D is feasible and then evaluate glucose metrics and PROs.

Hypothesis 1a: In phase 1, CGM use exceeding >50% of participants will be feasible and sustainable in youth with T2D, measured by days of CGM use per 2-week period (>75%). **H1b:** Following an additional needs assessment after phase 1, in phase 2 sustained CGM use per 2-week period (>75%) will exceed 75% of participants. **H1c:** Based on completion of PROs surveys, it is expected that diabetes-specific distress will decline, and overall well-being/quality of life will improve. Secondary outcome PROs (see protocol synopsis) collected at baseline will be associated with HbA1c and diabetes management outcomes. Data on glucose metrics, SDOH, and needs and barriers will be described.

Specific Aim 2: To assess the clinical outcomes (HbA1C, time in range [70-180 mg/dL], time in hypoglycemia [<70 mg/dL]) of individuals participating in this trial compared to clinic historical controls.

Hypothesis 2: Use of CGM will improve HbA1C and other clinical metrics of diabetes glucose control.

Measured Outcomes:

1. Sustained use of CGM by patients over one year measured by days of CGM use per every 2-week period with >80% as goal.
2. Change in HbA1C over first year of CGM use
3. Glucose profile metrics: percentage time in range, time in hypoglycemia, and time in hyperglycemia obtained from CGM.
4. Change in weight and BMI over first year of CGM use using clinic visit weight and BMI measurements.
5. PROs

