Data from the SEARCH for Diabetes in Youth study found that over 50% of youth with T2D had <3 SMBG per day and almost 25% had <1 daily¹⁵. Diabetes distress is well recognized as a factor that impacts both glycemic outcomes and diabetes self-care behaviors, such as SMBG¹⁶. The use of digital health tools and technology in T2D care has the potential to increase access but also to widen disparities in care, highlighting the need for further study of CGM use in youth with T2D. Use of CGM and digital health tools in Latinx adults with T2D has been shown to be effective in short-term pilot studies¹⁷. The benefit of CGM has expanded to adults with T2D using basal insulin only. In a recent randomized controlled trial of CGM use compared with SMBG in adults with T2D (53% minority race/ethnicity) showed a significant reduction in HbA1c of 0.4%, demonstrating benefit of CGM use in a broader population of adults with T2D¹⁸. The evaluation of CGM use in youth with T2D, with specific attention to factors that influence uptake and sustained use of diabetes technology in this population is necessary due to rising incidence of T2D in youth and higher rates of diabetes complications manifesting at earlier ages thereby depriving Latinx youth with T2D of a healthy future.

In the last few years continuous glucose monitors (CGMs) have become available for clinical use by children with type 1 diabetes as an alternative to self-monitoring blood glucoses. The use of CGM has consistently demonstrated an improvement in glycemic control and quality of life in youth with type 1 diabetes.^{19,20} CGMs are revolutionizing pediatric diabetes care with significant gains for youth with type 1 diabetes and are now the recommended standard of care for youth with diabetes.²⁰ CGM initiation in youth with type 1 diabetes is feasible and well accepted and our clinic is a leader in doing so.²¹ While there has been an exponential rise in CGM use in youth with type 1 diabetes, youth with type 2 diabetes who have similar SMBG and insulin requirements, have had little to no access to CGM. CGM use in adults with T2D has proven to be both efficacious and cost effective.¹²⁻¹⁴ However, our patients with T2D and public insurance (California Children's Services and/or Medi-Cal) have not been able to benefit from this technology due to a lack of insurance coverage for CGM in this patient population.

Preliminary Studies

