Significant improvements in HbA1C have been shown in youth with type 1 diabetes with public insurance with uninterrupted CGM use.²² This real-world data in youth with type 1 diabetes has complimented research study data and paved the way for earlier and easier CGM approval for youth, particularly publicly insured youth.

Our team has shown that youth with T1D with public insurance who have uninterrupted CGM use compared to those who lose CGM coverage due to insurance issues have significant improvements in HbA1c^{22,23}. This real-world data in youth with T1D has complimented research study data and paved the way for earlier and easier CGM approval for youth, particularly publicly insured youth. We aim to translate these learnings to our T2D population. In our clinic, youth with T2D have a mean HbA1c of 8.6% with only 35% at goal HbA1c of <7% (n=311 HbA1c values), indicating that the majority of youth with T2D are not meeting this significant diabetes therapy goal. Reflective of the national data demonstrating youth with T2D are overwhelmingly minorities and from families of lower SES, a significant portion of our T2D patient population (n=131) is publicly insured (77%), minority status (73% and Latinx 66%), and has Spanish-speaking parents or guardians (56%), all groups which have lower rates of diabetes technology use^{11,24}.

Design: This will be a two-phase pilot program focused on youth with T2D to evaluate initiation and sustained use of CGM. The focus of phase 1 will be a feasibility trial to use CGM in 30 youth with T2D and public insurance over a 12-month period. CGM will be provided to all participants. Education for youth and their families about CGM integration in diabetes care will be provided throughout the study. Barriers to CGM adoptions and sustained CGM use will be tracked throughout this phase to inform the further refinement of the program in phase 2 in 50 youth with T2D. As part of closing the disparities in diabetes technology use in youth with T2D, QoL and PROs will be evaluated. The goals of phase 2 are to utilize human factors design data, QoL and PRO metrics collected in phase 1 to address identified needs and barriers to increase initiation and continued use of CGM in this population.

Inclusion criteria

1. Diagnosis of T2D (diabetes autoantibody negative) followed in the Pediatric Endocrinology clinic at Stanford Children's Health

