2. HbA1C greater than 6.5% at enrollment. This is to enroll patients who are working on improving glucose control but are still not meeting HbA1c targets.^{9,25}
3. Interested in starting on a continuous glucose monitor
4. Access to a mobile device that is compatible with CGM applications or willing to use CGM receiver which will be provided. Both the receiver and mobile device allows patients to view glucose data and alerts from the CGM and upload glucose data during or in between in-person or virtual clinic visits, not necessitating that the participant have access to a mobile device.
5. Public insurance
6. Age 4-20 years inclusive

Exclusion criteria

1. Non-T2D diagnosis
2. HgA1C < 6.5%
3. Participant not willing to wear CGM
4. Private insurance

Procedures and Methods

Recruitment: The study team will review clinic schedules to identify youth with T2D from the patients in our clinic who would qualify. The informed consent process will be conducted prior to initiating the study. Following CGM initiation by a CDE, youth will have a routine 1-week clinic follow up with our diabetes team and then will be seen per clinic standard of care, every 3 months thereafter for the 12 months of the study duration. At each visit we will collect descriptive data on CGM use, CGM glucose metrics, and provide CGM supplies. PROs will be evaluated at three time points during the study. In phase 2, we will identify a new cohort of eligible patients who will be evaluated at a similar cadence as phase 1.

Visit	1	2	2a	3	3a	4	4a	5	5a	6
Weeks from start	x	2 weeks	4-6 weeks	12 weeks						
Informed consent and assent Visit Type ** this will be modified if LibreView App is available during study duration, can move visits to TH with lab A1C	x (can be done in person or via TH)									
	In person	IP/TH	phone/IP	IP	phone/IP	IP	phone/IP	IP	phone/IP	IP
Demographics	x									
Diabetes History	x									
HbA1C	x			x		x		x		x
CGM start	x				x					x
PROs	x			x						x
CGM metrics	x	x	x	x		x		x		x
CGM education	x	x	x			x		x		x
CRC check on supplies (confirm use and shipment)	x	x	x	x	x	x	x	x	x	x
Final study visit										x

Visit 1:

- Participants will be offered the opportunity to start on CGM at their scheduled clinic visit
- Participants will receive CGM education from a certified diabetes educator (CDE)

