At each visit we will collect descriptive data on CGM use, clinical glucose outcome metrics, and provide CGM supplies. Mixed affects modeling will be used to characterize the trajectory of measured variables and to account for patient-level correlation of this data. To account for gaps in CGM use we will use intention to treat analysis and consider a censoring method for a patient who leaves the practice or are lost to follow up. We will also perform an exploratory analysis of the relationship at a patient-level between days of CGM wear and time in range.

Study Timeline

Data Collection and Entry

1. Study participant data entry will be collected and entered in Stanford RedCap by the study team.
2. PRO will be collected in RedCap

The initial survey is filled out in person during the CGM visit during which, parents provide an email that will be the platform for contact for the future surveys. At the follow up points, the RedCap data base will automatically trigger survey link to the email on file. If the survey is not completed, a second email is sent as a reminder followed by provider team reminders. Participant data will be included for analysis for the time frames that are available when.

These measures will assess issues of adherence or illness distress and provide valuable information for providers to better understand the impact of early CGM initiation. The patient/guardian will have the option of filling out the questionnaires in English or Spanish. Based on the evidence in the PROs literature and our clinical experiences, we have developed an algorithm for responding to PROs screen scores that are outside of the normative range triggers a response from social worker and/or diabetes psychologist²⁷. Study personnel will complete a chart review to collect relevant health information including diagnosis, duration of disease, indicators of health status, and regimen information (e.g. medication, doses). These medical record data are required to assess the validity and usefulness of the clinical PROs screening measures. Additionally, reliability analysis will be conducted to examine the psychometric properties of the PROs measures, and the satisfaction questionnaire data will be aggregated to assess the acceptability of the PROs procedure from the patient's perspective.

- PROMIS global health (youth): BELOW 22 for the PROMIS global health scale. Anyone who scores 21 or lower would trigger an alert to place a diabetes psychology referral.

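### Aim 2 compares participants selected on interest in CGM and on HbA1c above 6.5% with undefined historical controls, with no adjustment planned, so a difference may reflect selection and regression to the mean

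*Combined protocol and SAP*

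**What the plan says.** Specific Aim 2 sets out to assess HbA1c, time in range and time in hypoglycemia "of individuals participating in this trial compared to clinic historical controls". Hypothesis 2 expects CGM use to improve HbA1c and the other glucose metrics, and the measured outcomes include HbA1c change over the first year of use.

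The inclusion criteria require HbA1c above 6.5% at enrolment, public insurance, age 4 to 20 and that the youth is "Interested in starting on a continuous glucose monitor". Unwillingness to wear CGM is an exclusion.

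The controls are mentioned only in Aim 2. No calendar period, entry rule, number or data source is given, and nothing says whether a participant's own earlier record may serve. Background and Significance says that the clinic's publicly insured patients with T2D "have not been able to benefit from this technology due to a lack of insurance coverage for CGM in this patient population".

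The Biostatistical plan covers descriptive statistics, GEE models for PROs and mixed models for trajectories. It gives no method for the historical comparison. In the visit schedule the only HbA1c before CGM is the one at Visit 1.

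On numbers, Design plans "a feasibility trial to use CGM in 30 youth with T2D and public insurance over a 12-month period" and then "further refinement of the program in phase 2 in 50 youth with T2D". Recruitment adds: "In phase 2, we will identify a new cohort of eligible patients". Preliminary Studies reports that "a significant portion of our T2D patient population (n=131) is publicly insured (77"%).

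**The concern.** Two features of entry can produce an apparent benefit without any CGM effect.

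- **Interest and willingness.** Youth who accept a device and a year of follow-up may have better HbA1c courses anyway. Earlier patients had no coverage, so they were not screened for interest in the same way.
- **The HbA1c threshold.** Participants enter on a value above 6.5%. Some of those values are temporarily high and will fall on repeat. Controls not held to the same rule at an index visit show no such fall.

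A third issue is overlap. If the controls come from recent clinic records, many may be the same patients as the participants, and a two-group analysis would treat them as independent.

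The results are to be taken to the public insurer to argue for coverage, so a wrongly attributed difference would matter.

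**Working it through.** The documents give no SD, power or sample-size figure for Aim 2, so there is nothing of the plan's own to reproduce. All bias sizes below rest on stated assumptions.

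**1. Pool and planned enrolment.** Publicly insured patients: 131 × 0.77 = 100.9, about 101. Planned participants: 30 + 50 = 80, and 80/100.9 = 79%. Under the contingency of 50 participants, 50/100.9 = 50%. This assumes a static roster and takes the enrolled share as the uptake.

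**2. Motivation bias against unscreened controls from the same pool.** Bias = r × SD × i(p). Here r is the correlation of willingness with one-year HbA1c change (assumed 0.1 to 0.3), SD is that of the change (assumed 1.5 points), and i(p) is the normal selection intensity φ(z)/p when the most willing fraction p enrols.

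| p | i(p) | Bias at r = 0.1 | Bias at r = 0.3 |
|---|---|---|---|
| 0.79 | 0.365 | 0.05 | 0.16 |
| 0.50 | 0.798 | 0.12 | 0.36 |

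A check without normality uses bias = (1 − p) × D, where D is the gap in mean change between interested and uninterested youth that is unrelated to CGM. At p = 0.79, a wholly spurious 0.4 to 0.5 points needs D = 0.4/0.21 = 1.9 to 0.5/0.21 = 2.4 points.

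**3. Regression to the mean.** The clinic reports a mean HbA1c of 8.6% with 35% of values below 7%. I fitted two skewed curves to those figures: a lognormal, and a lognormal shifted by 4.5. The repeat correlation ρ is assumed to be 0.6 to 0.9. The expected fall from a qualifying value is roughly (1 − ρ) × (mean above 6.5 − 8.6).

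| Curve | Mean above 6.5 | Formula, ρ = 0.9 to 0.6 | Simulated fall, no CGM effect |
|---|---|---|---|
| Lognormal | 9.88 | 0.13 to 0.51 | 0.11 to 0.47 |
| Shifted | 9.44 | 0.08 to 0.34 | 0.06 to 0.27 |

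The simulation sets ρ on the log scale. I quote its range as about 0.05 to 0.47, rounding the lower end down. Comparing an earlier value with a later one in the same simulated participants, leaving out the qualifying value, gives a difference of about 0.

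This bias applies to change from enrolment, which is the listed outcome. A comparison of 12-month levels would instead leave participants starting higher than unmatched controls.

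The ranges in steps 2 and 3 should not be added. The fitted curves have an SD of about 3.2, so the SD of change is 3.2 × √(2(1 − ρ)): 1.4 at ρ = 0.9 and 2.9 at ρ = 0.6. The assumed 1.5 therefore sits near the high-correlation end, where regression to the mean is smallest.

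**4. Overlap.** Suppose the controls' year ends at the same HbA1c value that starts the participants' year. With independent within-person errors of variance σ², equal groups of n and a fraction f of patients in both, the variance of the difference in changes is (4 + 2f)σ²/n, against 4σ²/n under independence. The SE ratio √((4 + 2f)/4) is 1.12 at f = 0.5 and 1.22 at f = 1. The reported SE is then 11% to 18% too small, and nominal 95% intervals cover 92% to 89%. This holds only for that layout, which the plan neither states nor rules out.

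**The case against.** The strongest reply is that high uptake helps the plan. If 79% of the pool enrols, little room is left for selection on motivation, and 0.05 to 0.16 points is well below the cited effects. That stands. A reader might infer from 80 of 101 that motivation alone could create the whole HbA1c difference, but the ratio points the other way. Its relevance is to overlap.

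Three other stronger readings also lack support:

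- **That participants asked for CGM.** The Visit 1 procedures say the clinic offers it. Interest is a condition of entry, not a request.
- **That controls were never offered it.** The text describes missing coverage and little or no access, nothing more.
- **That controls are the patients who declined.** On the same assumptions that comparison would give 0.24 to 0.78 points, but no section plans it. Former patients and earlier cohorts are neither participants nor refusers.

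It can also be said that the plan already includes within-participant change and mixed models. This is partly right, but the only scheduled pre-CGM value is the one at Visit 1. If that is also the qualifying value, the model carries the regression to the mean.

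Finally, a before-after contrast has its own limits. Youth who accept when their motivation rises would still bias it, and so would calendar trends or simultaneous education and coordinator contact. This is why it should stand beside the historical comparison and not replace it.

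**Conclusion.** The concern holds in a limited form. Participants are selected on interest, willingness and HbA1c, the controls are subject to no stated matching rule, and no adjustment is planned. A difference in HbA1c change therefore cannot be credited to CGM alone.

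The entry threshold is potentially the larger source. At low repeat correlation its bias reaches the size of the effects the protocol cites (0.4 points in adults with T2D, 0.5 in the clinic's T1D program). At high repeat correlation it is small. Motivation bias is modest at 79% uptake and grows if uptake is lower. These sizes depend on the assumed SD, correlations and fitted curves, none of which the documents supply. Overlap between the groups is plausible but not certain, because the control period is undefined and the roster will change.

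Aim 1 feasibility is unaffected. The change is worth making before the Aim 2 analysis.

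**What to change.** **Within-participant contrast.** The plan already states: "Study personnel will complete a chart review to collect relevant health information". Name HbA1c in that review and extract each participant's clinic values from the 12 to 24 months before Visit 1. Add to the mixed model a level change at CGM start that does not use the qualifying enrolment value as baseline. Estimate a slope change only where enough earlier values exist. Report this beside the historical comparison.

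**Historical comparison.** Take an index visit from calendar years before phase 1 recruitment, with the same insurance, age and HbA1c above 6.5% rules. Adjust for index HbA1c. Keep patients who later enrol and account for them with a patient-level random effect, entering each HbA1c value once. Excluding them would push the controls towards youth who did not volunteer. Describe the contrast as interested participants versus patients not screened for interest, and label it exploratory for Hypothesis 2.

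**Cost.** Protocol and SAP wording plus chart extraction, with no new visits. Participants with few or no earlier values, such as the newly diagnosed, add little. If the 311 clinic values belong to the 131 patients, which the text does not say, that is 311/131 = 2.4 each, or about 1.4 once a qualifying value is set aside. Neither contrast separates CGM from simultaneous education, coordinator contact or calendar trends, and the report should say so.

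### Minor: outcome 4 is one-year change in weight and BMI at ages 4-20 with no age- and sex-standardised measure and no comparator, so expected growth is part of the result, mainly for weight

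*Combined protocol and SAP*

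**What the plan says.** Measured Outcomes, item 4, reads "Change in weight and BMI over first year of CGM use using clinic visit weight and BMI measurements". It names the quantities and their source. Nothing in the document names a z-score, a percentile, a growth reference, or an adjustment for age, sex, puberty or height.

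The surrounding design is as follows.

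- **Age.** The inclusion criteria state "Age 4-20 years inclusive".
- **Follow-up.** After the first follow-up visit, participants are seen "every 3 months thereafter for the 12 months of the study duration" (Procedures and Methods, Recruitment).
- **Arms.** Phase 1 has 30 participants and phase 2 a new cohort of 50. In the Design section, "CGM will be provided to all participants".
- **Comparator.** Specific Aim 2 sets participants against clinic historical controls for "clinical outcomes (HbA1C, time in range [70-180 mg/dL], time in hypoglycemia [<70 mg/dL", and the list ends there. Weight and BMI are not in it.
- **Model.** The Biostatistical plan says "Mixed affects modeling will be used to characterize the trajectory of measured variables" and that patient-level correlation will be handled. It names no covariates for any outcome.

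**The concern.** Children and adolescents gain weight as they grow, whatever device they wear. Someone aged 4-20 at entry is between 5 and just under 22 a year later, so the eligible range runs from young children to adults who have stopped growing. A single-arm mean change in kilograms adds expected growth to anything else that happened in the year. A reader of the results cannot separate the two.

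Nothing in the plan removes growth from this outcome. There is no concurrent control, and the historical comparison does not cover it. The mixed model names no age or growth term. Even with baseline age added, the time slope in a single arm would still contain growth.

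What is at stake is limited. A mean weight gain during CGM use could be read as a consequence of CGM when part of it is growth, or a relative improvement in weight status could be hidden. No hypothesis or test is attached to this outcome.

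**Working it through.** The plan gives no effect size, SD or precision for weight or BMI, so there is no figure to reproduce. Only n = 30, n = 50, the age range and the 12 months come from the documents. **Every other input below is assumed**, and the results are an illustration.

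**Step 1. Weight gain from height alone.** Weight = BMI × height², so growth of g metres from height h at constant BMI adds BMI × ((h+g)² − h²).

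- Low end (BMI 30, 150 cm, 2 cm): 30 × (1.52² − 1.50²) = 30 × 0.0604 = 1.81 kg.
- High end (BMI 35, 160 cm, 6 cm): 35 × (1.66² − 1.60²) = 35 × 0.1956 = 6.85 kg.

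BMI change is zero in both cases by construction. Height growth therefore enters weight directly. It enters BMI only as far as expected BMI itself rises with age.

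**Step 2. Cohort mean drift.** Multiply by the share still growing. For BMI, assume an expected rise of 0.3-0.7 kg/m² per year in those growing.

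| Share growing | Weight drift (kg) | BMI drift (kg/m²) |
|---|---|---|
| 0% | 0 | 0 |
| 25% | 0.45-1.71 | 0.08-0.18 |
| 50% | 0.91-3.42 | 0.15-0.35 |
| 75% | 1.36-5.13 | 0.23-0.53 |

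**Step 3. Precision.** The 95% CI half-width for a mean change is t(0.975, n−1) × SD/√n. Assume an SD of 12-month change of 5-8 kg for weight and 1.5-2.5 kg/m² for BMI.

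| n | Weight half-width (kg) | BMI half-width (kg/m²) |
|---|---|---|
| 30 | 1.87-2.99 | 0.56-0.93 |
| 50 | 1.42-2.27 | 0.43-0.71 |

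**Step 4. Compare.**

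- *Weight, phase 1.* At 25% growing, the drift (at most 1.71 kg) is below even the smallest half-width (1.87 kg). At 50%, the top of the range (3.42 kg) exceeds the largest half-width (2.99 kg), while the bottom (0.91 kg) is well below the smallest.
- *Weight, phase 2.* At 25% growing, 1.71 kg exceeds the smallest half-width (1.42 kg) but not the largest (2.27 kg).
- *BMI, phase 1.* The largest drift (0.53) is below the smallest half-width (0.56) in every scenario.
- *BMI, phase 2.* At 50% growing, the drift (at most 0.35) is still below 0.43. It exceeds the half-width only at 75% growing, with BMI drift near the top of its range and SD near the bottom.

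**Step 5. Shorter follow-up.** Potential Pitfalls and Contingency Plans allows for 6 months of supplies. If follow-up were also 6 months and growth halved to 1-3 cm, the gain per growing participant would be 30 × (1.51² − 1.50²) = 0.90 kg to 35 × (1.63² − 1.60²) = 3.39 kg, about half the 12-month figure.

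**The case against.** The strongest reply is that this is a reporting detail. Outcome 4 is one of five measured outcomes in a single-arm pilot, carries no test, and drives no decision. BMI is reported beside weight and already adjusts for height. The item identifies a data source; it does not say that the values must be analysed unadjusted. The missing covariates are a general gap in the plan. A standardised BMI could be calculated at analysis, because clinic BMI already requires height and the plan includes a chart review ("Study personnel will complete a chart review to collect relevant health information").

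Most of this stands, and it is why the point is minor. The illustration is also sensitive to the age mix. With half the cohort growing and an SD of 5 kg, each growing participant must gain 1.87/0.5 = 3.7 kg from height alone to match the phase 1 half-width, or roughly 4 cm of growth at BMI 30 and 160 cm. If nearly all participants have stopped growing, the drift is close to zero.

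What does not stand is that a later calculation removes the gap. The plan defines the outcome as change in weight and BMI, and choosing a scale after seeing the data is what pre-specification prevents.

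A reader might infer more in three ways, none of which the documents support:

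- That growth would produce a falsely significant result. No test of zero change is planned for this outcome.
- That BMI is as affected as weight. The arithmetic shows that it is not.
- That the study's glycaemic or feasibility conclusions are compromised. They do not use weight or BMI.

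**Conclusion.** The point holds as a minor one. Followed as written, the one-year change in outcome 4 includes expected growth, and nothing planned takes it out. For weight, the mean drift could be anything from 0 kg to about 5 kg under the assumed inputs. It can match or exceed the precision of the estimate once a substantial share of the cohort is growing. For BMI it is about 0-0.5 kg/m², below the assumed phase 1 precision in all scenarios.

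That growth enters weight is arithmetic. Its size depends on assumed BMI, height, growth, share growing and SD, and on an age mix that the documents do not give. The consequence is confined to how this descriptive outcome is read.

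**What to change.** Add to Measured Outcomes, item 4: *and change from baseline to 12 months in one pre-specified age- and sex-standardised BMI measure (for example, percent of the 95th percentile) against a named reference.* State that this is the main weight-status result and that raw weight and BMI are reported descriptively for all participants. Participants beyond the reference's upper age limit at baseline or at 12 months contribute raw values only.

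The cost is a few lines of wording and a recalculation from height and weight that clinic BMI already requires, with no new visits.

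There are two limits to state in the plan. The standardised mean omits the oldest participants. Standardising also removes only average expected growth and does not make the remaining change attributable to CGM, since there is still no comparator for this outcome.
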